1.1.3.3 Clinical studies

AB103 has been evaluated in 2 safety and pharmacokinetic (PK) clinical studies, a Phase 1 study in healthy volunteers (study no. ATB-101) and a Phase 2 first-in-patients, proof of concept study (study no. ATB-201).

1.1.3.3.1 Phase I study ATB-101

The Phase 1 single center, randomized, double-blind, placebo-controlled, sequential-dose escalation study was conducted in 25 healthy volunteers. Four different escalating dose levels of AB103 were evaluated: $7.5 \ \mu g/kg$, $37.5 \ \mu g/kg$, $150 \ \mu g/kg$ and $450 \ \mu g/kg$ with a placebo control (1 or 2 subjects) included in each cohort; each subject received a single intravenous (IV) infusion of AB103 or placebo (saline) control. Blood was collected for PK and flow cytometry assessments of leukocyte subsets after infusions. Subjects were assessed 1-day and 6- to 8-days after the infusions for adverse events (AEs), vital signs, and clinical laboratory parameters. The primary objective of this study was to establish the safety profile and MTD of AB103 given as a single IV infusion in healthy volunteers. The secondary objective was to determine the PK profile of AB103 in humans after a single IV infusion. In addition, lymphocyte profiling was performed on subjects from the high dose cohort 4. Peripheral blood mononuclear cells (PBMCs) were obtained and subjected to flow cytometric analysis, for phenotypic analysis and intracellular cytokine expression. Study duration was 14 days.

A total of 22 AEs were reported during the conduct of the trial, of which 21 (95.5%) were mild and only one was moderate in severity. Of all the subjects in the study, 7 had AEs and 18 had no AEs. None of the AEs were considered related to Investigational Product. There were no dose-limiting toxicities nor were there any SAEs. There were no clinically meaningful changes in vital signs, clinical laboratory parameters, ECG parameters or lymphocyte subsets.

Lymphocyte profiling: Although variability between subjects was apparent, for the most part within a subject over time, the percentages of positive cells and absolute counts remained similar to those at baseline

PK in healthy subjects: Non-parametric pharmacokinetic parameters estimates are shown below:

Dose	C _{max}	AUC _{0-t}	T _{1/2}	CL
µg/kg	ng/mL	ng□min/mL	min	mL/min/kg
7.5	10.14 ± 2.22	61 ± 19	ND	ND
37.5	56.67 ± 30.28	523 ± 248	1.36 ± 0.51	85 ± 50
150	208.80 ± 51.37	2137 ± 370	1.26 ± 0.28	72 ± 11
450	707.74 ± 269.03	6082 ± 2022	1.34 ± 0.21	80 ± 22

Table 1: Summary of ATB-103 pharmacokinetic parameters in healthy volunteers

ND = not determined, insufficient data to calculate

Plasma AB103 concentrations in all cohorts peak near the end of the infusion and decline rapidly with a $T_{1/2}$ of a little over one minute. The apparent elimination $T_{1/2}$ was very similar

across dose levels. Systemic exposure to AB103 as measured by C_{max} and area under the curve (AUC) appeared to be dose-proportional. Consequently, plasma clearance (CL), which was derived from AUC and dose, was similar for all doses. The apparent volume of distribution, approximately 200 mL/kg, is much larger than plasma volume, which is consistent with distribution to sites outside the plasma compartment.

Summary: Overall, AB103 given IV at doses up to 450 μ g/kg was very well tolerated in healthy volunteers. Following a 10-minute IV infusion of AB103 to healthy volunteers, plasma concentrations peaked at the end of infusion and then decline rapidly with an apparent elimination half-life of a little over one minute. Exposure was dose-proportional.

1.1.3.3.2. Phase II study ATB-201

The Phase 2 study (ATB-201) was a multicenter, randomized, double blinded, first-inpatients exploratory study in subjects who had a clinical diagnosis of NSTI and scheduled to undergo urgent surgical exploration and debridement. The study was conducted in 7 clinical sites in the US, and included 40 patients. Patients were randomized to receive either AB103 as a single intravenous (IV) infusion of 0.50 mg/kg or 0.25 mg/kg, or placebo (saline), over 10 minutes. Study drug or placebo was administered within 6 hours from clinical diagnosis, in addition to SoC (including prompt and repeated aggressive surgical debridement, aggressive resuscitation and physiologic support, and antimicrobial drugs).

The study objectives were to determine safety and PK of AB103 and the potential treatment benefit compared to placebo, by clinical benefit (measured by resolution of systemic inflammatory parameters, resolution of organ dysfunction or failure, and the need for repeated surgeries for the primary infection), assess critical care/ pharmacoeconomic benefit by hospital length of stay, ICU length of stay/ICU-free days, vasopressors free days, and mechanical ventilation days/ free days, and define potential surrogate biomarkers. Study duration was 28 days.

Safety results: Safety was evaluated in the ITT population, comprised of all study participants who were randomized and received study drug or placebo (n=43). Due to the natural severity of the underlying disease, a high incidence of adverse events was expected in the study population. Patients in the High dose group presented with a more severe state of the disease, as exemplified by a higher rate of AEs, SAEs, and abnormal labs on Day 0 (before study drug administration). Post Day 0 (after drug administration) and over the course of the study, AEs were reported in 94.1%, 93.3% and 81.8% of patients in the High dose, Low dose and Placebo groups, respectively, with no statistically significant difference. No study drug-related AEs were reported. Most of the AEs were mild or moderate. Severe AEs were reported in 2 patients (11.8%) of the High dose group, 2 patients (13%) of the Low dose group and 3 patients (27.3%) of the Placebo group.

	SD	681	2.80	4,021	6.30	26.68	
	Median	899	5.00	8,497	2.61	29.42	

|--|

The PK studies in human confirm the short elimination half-life of the product, and that the systemic clearance (CLs) values demonstrate that the clearance processes involved are of high capacity and rate.

Efficacy results: Analysis of results from the Phase 2a study, indicated that patients in the AB103 treatment groups had a substantial improvement in their clinical status across

multiple endpoints when compared to patients in the placebo group. Patients in the AB103 0.50 mg/kg and AB103 0.25 mg/kg treatment groups had a continuous resolution of organ dysfunction over time without subsequent worsening. Although not statistically significant, AB103 treated patients had a trend of spending fewer days in ICUs, requiring fewer days of assisted ventilation, and needing fewer surgical procedures to remove necrotic tissue. In addition, treatment of patients with AB103 reduced the levels of both systemic and local tissue cytokines and chemokines in a dose dependent manner. Tissue biomarkers, especially in the margins of the lesion, had reduced levels of cytokines, suggesting that administration of high dose AB103 may reduce progression of inflammation in marginally involved tissues. The overall tissue and systemic biomarkers are consistent with the mechanism of action of AB103, as attenuating the inflammatory response and possibly reducing the zone of tissue injury. The summary of the results is presented in Table 3 below:

	Placebo	0.25 mg/kg	0.5 mg/kg
Days in ICU	8.9	4.9	5.4
Days on Ventilator	5.2	3.1	2.7
SOFA score Day 14*	2.7	1.1	0.7
% patients with organ failure at Day 14	40	14.3	7.1
(defined as SOFA score ≥ 3)			
% patients with organ dysfunction at Day 14 *	66.7	37.5	11.1
(defined as SOFA score ≥ 2)			
% of patients with only 1 debridement	20	26	33
% of patients with \geq 4 debridement	30	20	13
% Mortality	20	6.7	6.7

Table 3: Consistent response across multiple clinically relevant end points

*P<0.05

Based on the reproducibility of the dose response in the various parameters, the 0.5 mg/kg dose was chosen for further clinical development.

1.1.3.3.3 A retrospective, non-interventional analysis study ATB-201A

This study was set up to better understand and characterize the clinical course of the disease under SoC treatment. The main goal was to evaluate potential clinical outcome parameters and to assess their suitability for the pivotal Phase 3 study program. Within this context, the study reviewed clinical data from 198 patients receiving SoC in 2013 at 12 US clinical sites. In a second step, the results of this retrospective putative placebo population were compared to those from the placebo- and AB103-treated population in the Phase 2 Study AB-201. The retrospective analysis employed a new composite endpoint, defined as necrotizing infection composite clinical endpoint (NICCE). Responders to the NICCE are (i) alive at Day 28, (ii) have Day 14 debridements ≤ 3 (iii) had no amputation done after the first debridement, and (iv) have a Day 14 mSOFA (modified Sequential Organ Failure Assessment [SOFA] evaluating 5 organ systems not including the liver organ component) score ≤ 1 . The retrospective study demonstrated that early development of systemic organ dysfunction in patients with NSTI is associated with higher morbidity and mortality. Failure of resolution of organ dysfunction by Day 14 is also associated with poor outcome. mSOFA score may be a useful marker for patient selection for inclusion in interventional trials and the resolution of organ dysfunction by d14 may be an important clinical endpoint. The study confirmed that the suggested composite endpoint NICCE is a clinically relevant endpoint which is highly correlated with several meaningful and relevant clinical patient outcome. In addition, the analysis determined that a more severe NSTI population (defined by a baseline mSOFA score of \geq 3) demonstrate worse outcome compared to All-comers and would likely benefit most from AB103 treatment.

1.2 Risks and Benefit

Efficacy results of the Phase 2 study ATB-201 suggest that patients treated with AB103 in addition to the SoC can experience improved clinical outcomes as compared to SoC alone.

Patients randomized to receive placebo in the study will not benefit from the potential therapeutic effect of AB103, however they stand to benefit from the safety measures and close observation included in the study as detailed below.

No compensation, monetary or otherwise is offered to study participants except to cover customary cost of travel and/or meals associated with any study required visits that may occur after hospital discharge.

Safety of AB103 has been studied extensively in a set of non-clinical studies (section 1.1.3.2) in Phase 1 study of human healthy volunteers and in Phase 2a in NSTI patients (see section 1.1.3.3). In both clinical studies AB103 has demonstrated a good safety profile, and no specific drug-related safety concern has been identified to date.

This study protocol details several safety measures:

- Detailed exclusion criteria (Section 3.2) including:
 - Any concurrent medical condition, which in the opinion of the Investigator, may compromise the safety of the patient or the objectives of the study or the patient will not benefit from treatment such as:
 - CHF {NYHA class III-IV}
 - Severe COPD {GOLD stage III-IV. or chronic hypoxemia (PaO2 <55 mmHg) on room air, or chronic use of home ventilation, or unable to climb stairs or perform household duties due to chronic obstructive disease resulting in severe exercise restriction, or use of continuous home oxygen prior to hospital admission (sleep apnoea treated with continuous positive airway pressure or biphasic positive airway pressure oxygen during sleep is acceptable)}
 - Liver dysfunction {Childs-Pugh class C}
 - Immunosuppression (see Appendix F- Section 15.6 for list of excluded immunosuppressive medications)
 - Neutropenia < 1,000 cells/mm3not due to the underlying infection
 - Idiopathic Thrombocytopenic Purpura (ITP)
 - Receiving or about to receive chemotherapy or biologic anti-cancer treatment although hormonal manipulation therapies for breast and prostate malignancies are permitted
- Hematological and lymphatic malignancies in the last 5 years
 - Patients that are treated with continuous hemofiltration (e.g. CVVH) for acute kidney dysfunction, not due to NSTI, starting prior to study drug administration.
- Pregnant or lactating women; Female of childbearing potential must have a negative βsubunit hCG pregnancy test immediately prior to study entry.
 - Frequent follow-up visits
 - A medical monitor and Independent Data Monitoring Committee (iDMC) will monitor the safety aspects of the study (see sections 8.6).

1.3 Study Treatment

This is a blinded randomized clinical study in which each patient will receive a single treatment of either 0.50 mg/kg AB103 or placebo (0.9% Sodium Chloride sterile solution) administered intravenously at one of 2 time points: (A) during surgery or (B) shortly after surgery, as long as the administration will be at the earliest time possible and within 6 hours from the clinical diagnosis. Administration will be based on clinical diagnosis of bacterial NSTI at the study site and a decision for urgent surgical wound debridement, and upon confirming the diagnosis of NSTI during the debridement.

The intravenous infusion will be delivered by a syringe pump (may be manually pushed if approved by the medical monitor) over 10 minutes in a separate catheter than that used to deliver other medications. The syringe will identify the contents as "study drug" for protocol ATB-202. All study personnel and clinical staff, as well as the patient, shall remain blinded as to the actual composition of the study drug administered to a given patient. Only the assigned study pharmacist or authorized qualified designate preparing the drug shall be unblinded to the treatment.

1.4 Compliance Statement

This clinical study will be conducted according to the Declaration of Helsinki. The study will be conducted in compliance with this protocol, GCP (CPMP/ICH/135/95), designated SOPs, and with local laws and regulations relevant to the use of new therapeutic agents in the country of conduct.

1.5 Study Population

The study population will consist of patients with a clinical diagnosis of NSTI scheduled to undergo urgent surgical exploration and debridement. At the time of surgery, the diagnosis of NSTI shall be confirmed.

290 patients will be recruited into the study and randomized to either 0.5 mg/kg AB103 or placebo in a 1:1 ratio. Randomization will be stratified by the diagnosis of Fournier's Gangrene and magnitude of mSOFA score at screening categorized as 3-4 versus >4. In the retrospective study analysis set with baseline mSOFA \geq 3 (N=69), the median value was 4 and 46.6% had values larger than 4.

2. STUDY OBJECTIVES

2.1 Primary Objective

To demonstrate the efficacy of AB103 as compared to placebo, in patients diagnosed with NSTI, using a clinical composite success endpoint:

The NSTI clinical composite score, NICCE will be defined as the primary end point which will be composed of the following patient outcomes (i) Alive at Day 28, (ii) Day 14 debridements \leq 3 (iii) No amputation done after the first debridement (iv) Day 14 modified SOFA (mSOFA) score \leq 1 (mSOFA includes respiratory, cardiovascular, CNS, renal, and hematologic organ components but not hepatic/liver component) (v) Reduction of \geq 3 score points between Baseline and Day 14 mSOFA score.

Component	NICCE
Survival	• Alive at Day 28
Local component	 ≤3 debridements throughout Day 14 No amputation beyond first debridement
Systemic component	 mSOFA score of ≤1 at Day 14 Reduction of ≥3 score points between Baseline and Day 14 mSOFA score

To be considered a success, patients must meet all components of the NICCE. A two-sided α =0.01 will be used to test superiority of AB103 relative to placebo for the primary endpoint (NICCE).

Conditional co-primary end point:

To demonstrate the efficacy of AB103 as compared to placebo, in patients diagnosed with NSTI, using a modified clinical composite success endpoint that includes (i) Alive at Day 28, (ii) Day 14 debridements \leq 3 (iii) No amputation done after the first debridement. To be considered a success, patients must meet all 3 components of this modified composite endpoint.

The conditional co-primary end point will only be tested if superiority is demonstrated for the primary endpoint at a two-sided α =0.01 significance level in order to account for multiple comparisons. A two-sided α =0.05 will be used to test superiority of AB103 relative to placebo for the co-primary endpoint.

2.2 Secondary Objectives:

- To demonstrate the safety of AB103 when administered as a single dose of 0.50 mg/kg to patients diagnosed with NSTI
- To demonstrate the efficacy of AB103 as compared to placebo, in patients diagnosed with NSTI, using the 5 component clinical composite endpoint but with mSOFA ≤1 at Days 21 and 28

- Comparison of the distribution of mSOFA scores between treatment groups at Days 14 and 21
- Kaplan-Meier analysis of the time to resolution of mSOFA score to ≤ 1 with censoring at Day 14
- To demonstrate the efficacy of AB103 compared to placebo as related to the individual components of the NICCE in patients with NSTI
- To demonstrate efficacy of AB103 in relation to the critical care and hospital stay parameters:
 - a. ICU days
 - b. ICU-free days
 - c. Days on ventilator
 - d. Ventilator free days
 - e. Vasopressor days
 - f. Vasopressor free days
 - g. Hospital length of stay
- To demonstrate the efficacy of AB103 in patients with septic shock
- To determine the incidence of Stage 2 and 3 acute kidney injury (AKI) (using the KDIGO criteria) and compare the rates of complete recovery by Day 28 between the AB103 treated patients and the placebo treated patients
- Additional AKI endpoints:
 - To determine the incidence of Stage 2 and 3 AKI (using the KDIGO criteria) and compare the rates of complete and partial recovery by Day 28 between AB103 and placebo treated patient
 - Determine the incidence of Stage 1, 2 and 3 AKI and compare the rates of complete recovery between the AB103 and placebo treated patients
 - Determine the incidence of Stage 1, 2 and 3 AKI and compare the rates of complete and partial recovery between the AB103 and placebo treated patients
 - Calculate time to complete recovery from AKI
 - Calculate time to partial recovery from AKI
- To demonstrate the safety of AB103 in regard to secondary infections

2.3 Exploratory Objectives:

- To conduct an exploratory evaluation of the clinical response by baseline pathogen
- To evaluate microbiological outcome in the microbiological evaluable population
- To conduct an exploratory evaluation of plasma and urinary biomarkers in patients with AKI
- To conduct an exploratory evaluation of blood leukocyte transcriptome (RNA expression) profiling in patients with NSTI and compare genomic profile in patients treated with AB103 versus placebo
- To evaluate health economic and financial outcomes associated with the treatment
- To evaluate NICCE outcome in screen failure patients with baseline mSOFA = 2 and post-operative mSOFA \ge 3. Note: These patients will not be included in the

MITT population analysis (they will not receive blinded study drug) and only considered to be an observational cohort

• To evaluate the immunogenicity of Reltecimod (formerly AB103)

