4.3.11 Follow-up of Patients

Patients who received the study drug are required to complete the procedures outlined for this clinical study. Exceptions would only include the withdrawal of consent, lost to follow-up or death.

If a patient misses a scheduled visit, attempts to complete the patient data will be made via telephone or rescheduling the visit. After waiting one week for the response, a return-receipt, certified letter containing instructions to call for an appointment will be sent. If no response is obtained within one week after sending the return-receipt letter, the patient should then be considered as lost to follow-up. The returned receipt should be filed with the Investigator's copy of the patient's eCRF. A clinical evaluation should be made based on the last contact with the patient.

Serious Adverse Events (SAEs) occurring within 28 days of a patient receiving IMP will be recorded and processed as described in Section 8.4 of the protocol.

4.4 Sub-study mSOFA = 2

Projected number of patients 60. Note: These patients will not will not receive blinded study drug and are only considered to be an observational cohort.

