5.1 Baseline Comparisons

Demographic and baseline characteristics will be summarized for each analysis set overall and by treatment group. Categorical variables including race, ethnicity, and gender will be summarized by counts and percentages. Continuous variables will be summarized using mean, median, standard deviation (SD), and minimum and maximum values. Continuous variables evaluated will include age, BMI, height, weight, systolic BP, diastolic BP, MAP, heart rate, and temperature; as well as ANAYA, LRINEC, and APACHE II scores. Presence of baseline sepsis will be summarized according to the numbers and percentages of patients with baseline cardiovascular and respiratory organ failure as reflected in screening component SOFA scores of 3 or 4. In addition presence of any AKI at baseline algorithmically determined, Stage 2/3 AKI at screening, and maximal AKI Stage 2/3 as assigned by the blinded adjudication panel will be summarized.

Analyses will be performed to confirm that the randomization resulted in no clinically significant group differences at baseline. Although emphasis will be on clinical significance, baseline comparisons will include t-tests or Wilcoxon rank-sum tests as appropriate for interval variables and chi-square or Fisher's exact tests as appropriate for nominal variables to aid in the screening for baseline differences. If there are clinically important baseline differences, multiple logistic regression will be used in supporting analyses to assess the impact of the imbalance on significance levels.

5.2 mSOFA

The Sequential Organ Failure Assessment score or SOFA was originally developed to track a patient's status during a stay in an intensive care unit (ICU)⁸,⁹. Each of six organ systems are evaluated (see Appendix 5) with ordinal scores 0 to 4. A total score is the sum of the component scores. For this study, the liver component is excluded and the resulting sum score is referred to in this study as 'mSOFA'.

Several approaches will be taken to summarize changes over time and between treatment groups in the clinical scores as described below.

mSOFA scores will be assessed as 1) observed cases, 2) last observation carried forward (LOCF), 3) using MMRM, and 4) categorized and combined with mortality and local activity as part of the primary composite clinical success endpoint, NICCE.

The following will be defined as OBSERVED mSOFA.

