5.2.1 Mean and Mean Changes Over Time

Mean values (SD) for the mSOFA and for the 5 specific organ components will be summarized over time with and without last-observation-carried-forward (LOCF). Similarly, mean (SD) changes scores from both day 0 and day 1 will be summarized with and without LOCF.

5.2.2 mSOFA as Part of Primary Endpoint

The primary efficacy endpoint (NICCE) employs mSOFA in two of its five components. NICCE success requires mSOFA at Day $14 \le 1$ and the improvement from screening Day 0 to Day 14 that is ≥ 3 .

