8.5 Sensitivity Analysis Removing the Reduction in mSOFA Component

Table 14.2.1.8 provides a sensitivity analysis for the primary NICCE endpoint. In this analysis, the requirement that there be at least a 3 point reduction in mSOFA from screening to Day 14 is removed. This was the original formulation of the NICCE endpoint before FDA requested that that the reduction component be included for this trial.

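### NICCE cannot be achieved in the mSOFA = 2 observational cohort, because it requires a fall of at least 3 points from a baseline of 2

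*Protocol*

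**What the plan says.** - **Objective.** Protocol 2.3 plans "To evaluate NICCE outcome in screen failure patients with baseline mSOFA = 2 and post-operative mSOFA" of at least 3. The synopsis repeats this under its exploratory objectives and its exploratory measures, and Protocol 7.3 repeats it as a measure. Protocol 2.3 keeps these patients out of the mITT population and describes them as observational.
- **Cohort.** Protocol 4.4 gives "Projected number of patients 60" for the sub-study. Protocol 4.4.1 lists two separate assessments. One is a baseline mSOFA taken as in 4.3.1, before first surgery, with a total of 2 (two organs scoring 1, or one scoring 2). The other is a post-operative mSOFA.
- **Endpoint.** Protocol 2.1 lists five NICCE components. The fifth is a reduction of at least 3 "score points between Baseline and Day 14 mSOFA score". It adds: "To be considered a success, patients must meet all components of the NICCE". Protocol 7.1 and SAP 2.1.2 list the same five.
- **Reference score.** SAP 5.2.2 makes success depend on "the improvement from screening Day 0 to Day 14 that is" at least 3.
- **Four-component version.** The retrospective study in Protocol 1.1.3.3.3 used NICCE without the reduction criterion. SAP 8.5 keeps that version as a sensitivity analysis of the primary endpoint and says: "This was the original formulation of the NICCE endpoint before FDA requested that that the reduction component be included for this trial".

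**The concern.** The reduction criterion makes sense in the randomised trial, where entry requires a screening mSOFA of at least 3 and a fall of 3 is always arithmetically possible. Carried over to a cohort defined by a baseline of 2, it becomes a condition that nobody can meet. A patient who survives, has one debridement, has no amputation and has no organ dysfunction at Day 14 is still a NICCE failure.

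At stake is whether the sub-study can answer its own objective. It is meant to describe outcome in patients just below the entry cut-off who worsen after surgery, and NICCE is the only outcome the objective names. These patients consent and have repeat blood counts and creatinine measurements for it. An analyst who follows the text must report a rate fixed in advance; one who sees the problem must choose a different definition after the data are in.

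**Working it through.** The plan states no figure for this cohort, so there is none to reproduce. The check is a direct enumeration.

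**Inputs**
- Reference score B = 2: Protocol 4.4.1 calls it baseline, and SAP 5.2.2 takes the fall from screening Day 0.
- Range of mSOFA: SAP 5.2 says "Each of six organ systems are evaluated (see Appendix 5) with ordinal scores 0 to 4" for SOFA, and mSOFA drops the liver. Five organs scored 0 to 4 give a total from 0 to 5 × 4 = 20.
- Systemic part of NICCE: Day 14 score D ≤ 1, and B - D ≥ 3.

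**Baseline of 2, as the text reads**

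| D | B - D | D ≤ 1? | B - D ≥ 3? | Systemic part met? |
|---|---|---|---|---|
| 0 | 2 | yes | no | no |
| 1 | 1 | yes | no | no |
| 2 | 0 | no | no | no |
| 3 to 20 | -1 or lower | no | no | no |

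No value of D from 0 to 20 meets the rule, so the success probability is 0 however many patients are in the subset. The missing-data rules do not help. Scoring an unmeasured organ as 0, or carrying a score forward, cannot take the Day 14 total below 0.

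**Same rule with other reference scores**
- B = 3: only D = 0 passes (3 - 0 = 3).
- B = 4 or more: D = 0 or 1 passes (4 - 1 = 3).

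**Reduction criterion removed**
- D = 0 or 1 passes the systemic part, whatever the baseline.

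The impossibility therefore comes only from pairing the reduction criterion with a reference score of 2. Changing either one removes it.

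**Does any text change either one?** SAP 4.5 (exploratory endpoints), SAP 4.6 (subgroups) and the table list in SAP Appendix 1 contain nothing on this cohort. Table 14.2.1.8, which reports NICCE without the reduction, is for the mITT set by treatment group, and this cohort is outside mITT. Protocol 4.4 does not mention NICCE.

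**The case against.** **The post-operative score may have been meant as the reference.** Protocol 2.4 glosses baseline as pre-treatment. In the main trial the drug may be given after surgery within 6 hours of the decision to operate, and 4.4.1 times the post-operative mSOFA in that same window. The objective selects on this score being at least 3, from which a fall of 3 is possible. This is a plausible intention, but it is not written down. Protocol 2.3 and 4.4.1 call the 2 the baseline and the later value post-operative, and SAP 5.2.2 takes the fall from screening Day 0. SAP 5.2 also removes Glasgow Coma scores inflated by ventilation or medication from the screening mSOFA only, so using a post-operative reference would still need new text.

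**NICCE may mean the four-component version here.** Protocol 1.1.3.3.3 uses the name that way, and Protocol 2.2 spells out the five components for one secondary objective, whereas the sub-study objective says only NICCE. The label is indeed used in two ways. But 2.1, 7.1 and SAP 2.1.2 define NICCE for this trial with five components, and nothing exempts this cohort.

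**It is exploratory and untreated, and no table is planned.** This stands and limits the importance of the point. It does not make the objective answerable as written.

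**Readings that go too far**
- A reader might infer a result of 0 out of 60. The 60 covers the whole mSOFA = 2 sub-study. The objective covers only those whose post-operative score also reaches 3, and that number is not given.
- A reader might infer that the plan sets this cohort against the randomised arms, or against the untreated rates quoted for patients with mSOFA of 3 or more (33.3%, 23/69, in Protocol 9.1.2; 30.4%, 21/69, in SAP 2.4.1). Neither document plans such a comparison.
- A reader might infer that the sub-study yields nothing. The individual components can still be described.

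**Conclusion.** The point holds. On the documents' own definitions, NICCE success is 0% by construction in screen failures with baseline mSOFA = 2 and post-operative mSOFA of at least 3: the largest possible fall is 2 and the requirement is 3. This rests on two readings, that NICCE means the five-component endpoint and that the fall is taken from the pre-operative score of 2. Both are what the text says, and no passage states an alternative for this cohort. If the sponsor intended an alternative, it still has to be written down.

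The effect is confined to an exploratory observational cohort of unstated size. The primary and co-primary analyses, alpha and power do not depend on it. The change is worth making because the plan, followed literally, gives an uninformative answer to the only outcome the objective names, and the remedy is cheap.

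**What to change.** 1. In the synopsis (exploratory objectives and exploratory measures), Protocol 2.3 and Protocol 7.3, state that this cohort is evaluated on the four-component NICCE: alive at Day 28, no more than 3 debridements to Day 14, no amputation after the first debridement, and Day 14 mSOFA of 1 or less. Protocol 1.1.3.3.3 and SAP 8.5 already supply this component list. Section 4.4 does not name NICCE and needs no change on this point.
2. Add a separate descriptive SAP table for this cohort, with its denominator defined as patients with baseline mSOFA = 2 and post-operative mSOFA of at least 3. Table 14.2.1.8 cannot serve, because it is restricted to mITT.
3. If the cohort is shown beside the placebo arm, score that arm on the same four components.
4. A fall from the post-operative score may be described secondarily, labelled as not comparable with the pre-operative baseline of the main trial.

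**Cost.** One clarifying statement in four places in the protocol and one SAP table. No new data are needed: operative procedures, amputations, Day 14 mSOFA and survival are collected under 4.4.1 to 4.4.4. The downside is that the cohort is not reported on the exact five-component primary endpoint.
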